7.7.1. Patient characteristics

[figure not shown]
Primary objective 1:

Demographical and clinical variables of RCC and mRCC patients will be summarized at index. Treated and non-treated mRCC patients will be analysed separately. For laboratory measures and performance status, the closest available measure +/- 90 days from index will be utilized. In case of a high rate of missing values, the time window can be extended to 6 months.

The demographical and clinical variables include but are not limited to:

- age at index
- sex
- history of renal insufficiency (any records until index)
 - ICD-10 code: N17-N19
- history of dialysis (any records until index)
 - procedure codes: TK800, TK829, TK810,
 - ICD-10 code: Z49

PFIZER CONFIDENTIAL

- history of kidney transplant (any records until index)
 - procedure codes: KAS10, KAS20
 - ICD-10 code: Z94.0
- history of nephrectomy (any records until index)
 - procedure codes: KAC*, KAD*, KAS40, KAS41
 - ICD-10 code: Z90.5
- performance status at index
 - Karnofsky (converted from Zubrod/ECOG)
- time from initial diagnosis of RCC to initiation of treatment for metastatic RCC
- various laboratory measures (e.g. hemoglobin, serum calcium, neutrophiles, thrombocytes, creatinine, albumin, eGFR)
- smoking status (if available in structured format)
- histology (if available in structured format)
- BMI (if available in structured format)

For categorical variables, the number (N) and the proportion (%) of patients in each class will be reported. For continuous normally distributed variables, mean and standard deviation (SD) will be reported. For continuous, non-normally distributed variables, median, the 1st quartile and the 3rd quartile will be reported.

The difference between strata will be tested using chi-squared/Fisher's exact test (categorical variables), t-test (continuous normally distributed variables) and Kruskal-Wallis test (continuous non-normally distributed variables).

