5. RATIONALE AND BACKGROUND

Renal cell carcinoma (RCC) is among the 10 most frequently occurring cancers and the most common type of kidney cancer occurring in Western communities [1]. RCCs comprise a heterogeneous group of malignant neoplasms arising from the nephron. Risk factors for RCC include obesity, hypertension, cigarette smoking, diet, diabetes, and male gender [1].

After decades of increasing trends in RCC incidence and mortality rates, it seems that rates are stabilising or starting to decline in many Western countries [1]. The worldwide number of kidney cancer cases was 431,288 (62.9% male) and deaths 179,368 (64.4% male) in 2020 [2]. Kidney cancer is more common in males compared to females. The incidence was 7.8 and mortality 3.0 per 100,000 males in high human development index countries in 2020 [2]. In Finland, the number of new kidney cancer cases was 635 in males and 353 in females in 2019 [3], and the number of prevalent patients was 4,943 males and 3,867 females in 2019 according to the Finnish Cancer Registry [4].

Localized RCC can be curatively treated with nephrectomy. However, about 20–30% of patients present with metastatic RCC (mRCC) at the time of diagnosis [5]. In addition, another 20% of patients with localized RCC undergoing nephrectomy will have a relapse and develop mRCC during follow-up. Despite the recent advances in mRCC treatment, metastatic disease is often fatal [6].

[figure not shown]
Over the last decade, the treatment of advanced/metastatic RCC has been constantly evolving, especially in the last 2-3 years with the emergence of several novel treatment options in rapid succession. Current recommendations for first-line therapy of mRCC include several combination treatments, superseding the previously recommended antiangiogenic agent monotherapies. The novel options combine an anti-PD-1-antibody with either an antiangiogenic drug (vascular endothelial growth factor receptor (VEGFR) tyrosine kinase inhibitor (TKI)), or an anti-CTLA-4-antibody. The combination treatments are recommended

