7.2. Setting

The target population of this study is adult patients with RCC and medical records available at HDSF data lake. Estimated number of patients in this study is 220-550. The inclusion criteria is a diagnosis of renal cell carcinoma (ICD-10: C64) between January 2010 and December 2021 (Figure 1). Advanced/metastatic disease stage (mRCC) will be assessed based on ICD-10 diagnosis code for metastasis (C77*-C79*), American Joint Committee on Cancer (AJCC) stage 4, visit to oncologist (specialty code 65), or initiation of treatment for mRCC.

[figure not shown]

Figure 1. Graphical illustration of study time windows and corresponding analyses.

The data collected has been generated as part of standard clinical care, treatment, and follow-up of patients with RCC. In accordance with the Finnish Act on Secondary Use of Health and Social Data 552/2019 (in Finnish: Laki sosiaali- ja terveystietojen toissijaisesta käytöstä), health registry data can be processed in scientific studies without patient consent. The purpose of this act is to establish conditions for the effective and secure processing of, and access to, personal health and social data for certain secondary purposes, such as research and statistics, innovation and development, knowledge management, teaching and authority planning. Thus, the Secondary Act creates a clear legal basis for the use of such registered data for research and innovation related to, for example, the health and well-being of citizens, the prevention of

disease and the development of new treatment methods. This relatively new legislation is also a welcome unification of the fragmented Finnish national rules regarding the use of healthcare and social welfare data. In addition, it takes into consideration current data protection requirements.

In the primary objective 1 (characteristics), all RCC patients will be analysed (local and metastatic diseases separately), while in the other objectives only treated mRCC patients will be analysed. Therefore, there are two cohorts to be analysed: 1) characteristics cohort (including all RCC patients), 2) mRCC cohort (including only treated mRCC patients).

Definitions for mRCC cohort

Index: Date of the first mRCC diagnosis; date of the metastatic disease identified as first of the following after the initial RCC diagnosis

- ICD-10 diagnosis code (C77*-C79*) for metastatic disease
- AJCC stage 4
- Visit to oncologist (specialty code 65) with RCC as main diagnosis

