- Treatment initiation for mRCC (sunitinib, pazopanib, cabozantinib, ipilimumab, nivolumab)

When analyzing the treatment outcomes, index is defined as the date of the treatment initiation.

End of follow-up (whichever of the following occurs first):

- Death
- Moving outside of HDSF
 - Approximated using data of healthcare contacts; no contacts to specialty care of HDSF within 2 years (patient censored at the last recorded visit)
- End of study (31.12.2021)

Length of follow-up (in years): ('end of follow-up' – 'index' + 1)/365.25

Definitions for characteristics cohort

Index:

- For mRCC patients, same as for the mRCC cohort (i.e. approximated metastasis date)
- For RCC patients, the date of the first record of RCC diagnosis (ICD-10: C64)

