7.2.2. Exclusion criteria

For the **characteristics cohort**, patients meeting any of the following criteria will be excluded from the study:

- Prevalent mRCC patients (i.e. diagnosis of metastatic RCC before 1.1.2010)
- Prevalent RCC patients (i.e. diagnosis of RCC before 1.1.2010) if there is no records of metastatic disease during 2010-2021

For the **mRCC cohort**, patients meeting any of the following criteria will be excluded from the study:

- Prevalent patients with mRCC (i.e. diagnosis of metastatic RCC before 1.1.2010)
 - Note that patients with local RCC before 2010 are included in this study if the disease has metastasised during 2010-2021
- Patients without treatment for mRCC (see Table 3 for details)

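### The until-index nephrectomy variable closes at diagnosis in local RCC but at metastasis in mRCC, so the local share is understated by an unknown amount and cannot be compared with the mRCC share

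*Combined protocol and SAP*

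**What the plan says.** Section 7.7.1 sets the time point for primary objective 1: "Demographical and clinical variables of RCC and mRCC patients will be summarized at index". Among the listed variables is "history of nephrectomy (any records until index"), identified from procedure codes and one ICD-10 code.

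The index is defined by group in section 7.2:
- Local RCC: "For RCC patients, the date of the first record of RCC diagnosis (ICD-10: C64").
- mRCC: "For mRCC patients, same as for the mRCC cohort (i.e. approximated metastasis date").

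Section 7.2.2 excludes "Prevalent RCC patients (i.e. diagnosis of RCC before 1.1.2010) if there is no records of metastatic disease during 2010-2021", so the local group holds only cases first diagnosed in 2010 or later, and its index is the start of the recorded disease. Section 7.2 states that "all RCC patients will be analysed (local and metastatic diseases separately"), so the two shares will be reported alongside each other.

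The only allowance after index in section 7.7.1 is for other variables: "For laboratory measures and performance status, the closest available measure +/- 90 days from index will be utilized". Section 5 gives the clinical role of the operation: "Localized RCC can be curatively treated with nephrectomy".

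**The concern.** Nephrectomy differs from the other history items in the list. Renal insufficiency, dialysis and transplant are conditions that a patient brings to the diagnosis. Nephrectomy is a treatment of the index disease. In local RCC the window closes on the day the disease is first coded, so an operation done because of that diagnosis counts only if C64 was first entered on or after the operation date (taking the index day as included). To that extent the variable records the order of coding rather than whether surgery took place.

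In a patient who progressed from local disease, the same wording runs up to the metastasis date and does pick up the earlier operation. In a patient metastatic at diagnosis, an operation after the mRCC index is missed. One label thus covers different quantities in groups that a reader will set side by side. At stake is a named clinical characteristic in a primary-objective table.

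**Working it through.** **The plan's own figure.** The plan gives no nephrectomy rate or timing. Its one derived figure, the mRCC cohort size in section 7.5, reproduces: 1,100 x 0.20 = 220 and 1,100 x 0.50 = 550. It does not bear on this point, which turns on definitions.

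**Definitions side by side.**

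| Group | Index (7.2) | Nephrectomy counted | Nephrectomy missed |
|---|---|---|---|
| Local RCC | First C64 record | Dated on or before that record | Any operation after it |
| mRCC, progressed from local disease | Approximated metastasis date | Operation for the earlier local disease | Any operation after metastasis |
| mRCC at diagnosis | Approximated metastasis date, close to diagnosis | Only if dated on or before index | Any operation after index |

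**Does another part of the plan recover the missed operations?**
- The 90-day allowance in 7.7.1 covers laboratory values and performance status only.
- Section 7.7.4 collects kidney procedures before and after mRCC diagnosis, but sections 6 and 7.2 restrict every objective other than primary objective 1 to treated mRCC. Local RCC and non-treated mRCC are not recovered.
- Table 2 assigns dated procedures, including nephrectomy, to primary objective 1. The data needed for a repair are therefore already requested.

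**Size, by assumption only.** Let t be the true share of local patients operated on, and f the fraction of those operations dated on or before the first C64 record. The reported share is t x f.
- t = 0.80: f = 0.10 gives 8%; f = 0.25 gives 20%; f = 0.50 gives 40%; f = 0.75 gives 60%; f = 1 gives 80%, with no loss.
- Over t = 0.80-0.95 and f = 0.10-0.60, the range is 0.80 x 0.10 = 8% to 0.95 x 0.60 = 57%.

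**When would the local share look lower than the mRCC share?** With m the share captured in mRCC, this happens when f < m/t. For t = 0.80 and m = 0.70, the threshold is 0.70/0.80 = 0.875. For m = 0.50 it is 0.50/0.80 = 0.625. None of t, m or f is in the documents.

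**IMDC strata.** Section 7.2.3 applies IMDC category to all primary objectives, and 7.7.1 tests differences between strata. One IMDC factor is less than a year from initial RCC diagnosis to start of treatment for metastatic disease. Patients metastatic at diagnosis who start treatment within a year score that factor and cannot be in the favourable category. They are also the patients whose operation can fall after the mRCC index. Under-capture can therefore differ between categories that are tested; how much cannot be determined.

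**The case against.** The strongest reply is that the item is labelled a history and summarised at index, which is a coherent baseline definition. The variable list is expressly open-ended and the dated procedures are available, so a treatment row can be added without redefining anything. This stands, and it is why the fix keeps the until-index row. It does not make that row informative about surgery in local RCC or comparable across groups.

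It is also fair that the main purpose of the study is mRCC, that nephrectomy is not a named Cox covariate in 7.7.3, and that 7.7.4 covers later kidney procedures in treated mRCC. These points limit the impact.

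A reader might infer three stronger conclusions that the documents do not support:
- **That most local nephrectomies are missed.** This is plausible, since treatment follows diagnosis, but nothing is said about when C64 is first coded relative to surgery. At f = 0.60 most would be counted.
- **That the table would reverse the true direction.** The plan states no expected direction and no rate in either group. Reversal depends on f, t and m, all unknown: a local share of 57% against an mRCC share of 50% shows none.
- **That a planned test would declare the artefact a finding.** Section 7.2.3 names IMDC category and treatment line as strata, with treatment line applied only to primary objectives 2 and 3. IMDC category is defined at first treatment for metastatic disease and cannot classify local RCC. No local-versus-mRCC test is specified.

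The loss in mRCC is uncertain too. The 20-30% in section 5 is the share metastatic at diagnosis, not the share operated on after index. Section 7.2.1 says metastatic codes are rarely used and relies on the oncologist visit as a proxy, so the mRCC index may itself fall after surgery.

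**Conclusion.** The point holds as a defect in a descriptive variable. Followed as written, the plan yields a local RCC nephrectomy share that omits every operation dated after the first C64 record, and that is not comparable with the mRCC share reported alongside it. The understatement cannot be computed from the documents; the 8-57% range against an assumed true 80-95% shows only how sensitive the figure is to coding order. Operations after index in patients metastatic at diagnosis are also missed, and this may affect the IMDC strata unequally.

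The conclusion rests on the index definitions and on reading the window as closing on the index day. It does not rest on any assumed rate, except that some local operations are dated after the first C64 record. Severity is minor to moderate.

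**What to change.** In section 7.7.1:
- Keep nephrectomy until index, labelled as a history variable.
- Add for all groups a row for nephrectomy at any time from before the initial RCC diagnosis through a common stated period after it. Twelve months is an example, an assumption to be confirmed with the clinical expert.
- For mRCC, also report nephrectomy up to the start of first-line treatment (treated) and within a stated period after the mRCC index (non-treated).
- Footnote the different index dates, and make no local-versus-mRCC comparison of the until-index row.
- Leave renal insufficiency, dialysis and transplant as they are.

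The cost is a few lines of text and extra date filters on procedures already extracted for primary objective 1. The downside is small: the period after diagnosis or index is shortened by death, loss of contact or indexing late in 2021. Footnote this too.

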7.7.2. Treatment patterns and treatment lines

Primary objective 2:

The treatment lines will be defined using drug administration and prescription data. The treatment options and lines will be visualized using Sankey plots and the proportion of patients per treatment type will be reported.

In general in mRCC, line of treatment (LOT) changes when the active substance changes, as the treatments are mainly monotherapies and only a few options consist of two substances (e.g. combination of ipilimumab and nivolumab in 1L).

The treatment lines will be defined *post hoc* using following process:

- For each active substance, single administrations/prescriptions are merged to treatment continuums.
- To identify, whether the treatment is monotherapy or combination of two active substances, the first records of the active substances will be considered

- if the first records of the two active substances are within 28 days, the treatment is considered as combination therapy of these two medications
- otherwise the two active substances are considered as two separate treatment lines
- The initiation of the treatment line is defined as the date of first record (dosing or prescription) of the active substance.

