7.7.3. Treatment outcomes

Primary objective 3:

The treatment outcomes will be assessed using time-to-event analysis, namely Kaplan-Meier fit or other relevant competing risk models. For each outcome, the time will be defined as follows (Figure 3):

- overall survival:
 - time from index until death (event) or end of study (censoring event)
 - when analysing by treatment lines, start the time from initiation of each treatment line
- progression free survival (PFS, defined using time to next treatment (TTNT) proxy):
 - time from initiation of the current treatment line until the initiation of the next treatment line (event), death (competing risk/event), or end of study (censoring event)

The Kaplan-Meier fits will be visualized, and the median survival/PFS of the patients will be reported as well, if reached.

Additionally, corresponding Cox proportional-hazards model will be fitted, including clinical variables as covariates (including but not limited to age, sex, IMDC risk score, diagnosis year, and treatment line number). The hazard ratios, 95% confidence intervals and p-values corresponding to each covariate will be reported.

[figure not shown]

Figure 3. Graphical illustration of definitions of treatment outcomes. Abbreviations: LOT = line of treatment.

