7.9. Limitations of the research methods

All the data is recorded by the hospital during everyday practice and most of the data is stored in structured format. Therefore, rather high quality of the data is expected. However, as with all RWD, it is plausible to have erroneous entries. Also due to the retrospective nature of the study, missing and/or incomplete data is expected in some of the medical records. Patients' records will not be excluded because of missing values, and missing data will not be imputed, i.e. the data will be analyzed as they are recorded in the electronic medical records. The proportion of missing values per variable will be reported.

The treatment lines will be defined based on the medication data and therefore, misclassification of treatment lines is possible. However, the start and end dates of each main drug are expected to be recorded rather precisely, and the clinician PPD will be consulted when constructing the treatment lines. Thus, the majority of the treatment lines are expected to be defined correctly.

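### Section 7.7.2 contradicts itself on return to an earlier drug, and its operational steps would miss or delay the next-treatment event

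*Combined protocol and SAP*

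**What the plan says.** Section 7.7.2 of the protocol opens with a general principle: "line of treatment (LOT) changes when the active substance changes". It then lists the process by which lines will be built, post hoc, from administration and prescription data:

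- Merging: "For each active substance, single administrations/prescriptions are merged to treatment continuums".
- Combination or monotherapy, judged from the first records of each substance: "if the first records of the two active substances are within 28 days, the treatment is considered as combination therapy of these two medications". Outside that window, the plan assigns one line to each substance.
- Start of a line: "The initiation of the treatment line is defined as the date of first record (dosing or prescription) of the active substance".

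No gap length closes a continuum, and no sentence covers a drug that comes back after another drug.

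Section 7.7.3 defines the PFS proxy (TTNT) from the start of one line to the start of the next. Death is a competing risk or event, and end of study is censoring. OS by line also runs from each line's start, and the Cox models include treatment line number as a covariate.

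Section 7.9 concedes that "misclassification of treatment lines is possible" and says that a clinician "will be consulted when constructing the treatment lines". It does not mention re-use.

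**The concern.** Merging, the combination test and the line start are all tied to the substance and not to a course of treatment. A programmer who follows the bullets gives each drug a single start date, so a return to an earlier drug starts no line. A programmer who follows the opening principle starts a new line at the same record. Two faithful implementations could therefore give different primary results.

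The lines feed the treatment sequences and Sankey plots (primary objective 2), TTNT and OS by line (primary objective 3), the line-number covariate in the Cox models, and resource use by line (secondary objective 2b). Under the operational steps, the line just before a return has no event at the return. Its TTNT runs on to a later new drug, death or end of study.

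**Working it through.** **Inputs from the documents.** The rules in 7.7.2 and the TTNT definition in 7.7.3. The only planning figure is the mRCC cohort size in 7.5, which reproduces (1,100 × 0.20 = 220; 1,100 × 0.50 = 550) but does not bear on this point. No re-use frequency and no TTNT are given.

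**Step 1: test sequences.** The operational steps were applied literally (one start per substance, 28-day combination window) and compared with the principle that a switch of substance changes the line. The days are invented for the test.

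| Sequence (start days) | Lines, operational steps | Lines, principle |
|---|---|---|
| Sunitinib 0, nivolumab 300, sunitinib 520 | 2 | 3 |
| Same, then cabozantinib 720 | 3 | 4 |
| Ipilimumab + nivolumab 0, sunitinib 220, nivolumab 420 | 2 | 3 |
| Ipilimumab + nivolumab 0, then nivolumab alone | 1 | 1 |
| Sunitinib 0, long break, sunitinib 700 | 1 | 1 (2 only if a gap rule is added) |

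Row 1: under the principle, line 2 has an event at 520 − 300 = 220 days. Under the operational steps it has none at that point.

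Row 2: line-2 TTNT is 720 − 300 = 420 days instead of 220, and cabozantinib is numbered line 3 instead of line 4.

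In both rows, first-line TTNT is 300 days either way, and OS from lines 1 and 2 has the same start and end either way.

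**Step 2: illustrative size, constant hazards.** Assume a next-treatment hazard of 0.06/month, a death hazard of 0.03/month, and a share p of next treatments that are unseen returns. The median time to next treatment or death is ln 2 / (0.06(1 − p) + 0.03).

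- p = 0: 0.693/0.090 = 7.7 months
- p = 5%: 0.693/0.087 = 8.0 (0.090/0.087 = 1.03)
- p = 10%: 0.693/0.084 = 8.3 (0.090/0.084 = 1.07)
- p = 20%: 0.693/0.078 = 8.9 (0.090/0.078 = 1.15)

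**Step 3: simulation.** Assume means of 10 months to next treatment and 20 months to death, uniform censoring over 0–60 months, and the same hazards again after an unseen return.

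| Re-use share | Median (months), returns counted → not counted | Fall in next-treatment events |
|---|---|---|
| 5% | 4.62 → 4.78 | 2.1% |
| 10% | 4.62 → 4.95 | 4.2% |
| 20% | 4.64 → 5.32 | 8.3% |
| 30% | 4.60 → 5.65 | 12.6% |

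Among patients with an unseen return, about 58% later had a new-drug event, 29% died first and 13% were censored.

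Steps 2 and 3 agree in relative terms because both assume next treatment to be twice as frequent as death (0.06/0.03 = 2; 0.10/0.05 = 2). The agreement is not independent confirmation.

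**The case against.** A reader might infer that re-use never starts a new line and that the TTNT event is always lost. The documents do not support that. Section 7.7.2 does not say that all records of a drug form one continuum; its plural leaves room for several per drug. Its opening principle gives three lines for A-B-A. The event is also often delayed, or replaced by death, and not lost altogether.

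A reader might also infer that every TTNT is too long. First-line TTNT does not change under A-B-A. From line 3 on, the direction is open: in A-B-A-C, line 3 is C under one reading and the return to A under the other, so different courses are compared.

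Clinician consultation is part of constructing the lines (7.9), and 7.8 adds a plausibility check. Both could catch some cases.

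These points limit the claim but do not remove it. The principle is introduced as a general statement, and the bullets are what will be programmed. Even if several continuums per drug are intended, nothing separates them, and the start is still dated from the substance's first record. The clinician is given no written rule on re-use, so that step does not settle which reading applies.

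**Conclusion.** The concern holds as an internal inconsistency. The principle makes A-B-A three lines; the operational steps, read literally, make it two. Under the operational steps, TTNT for the line just before the return can only be too long. Later lines are under-counted or misnumbered, which affects the Sankey plots, TTNT and OS for line 3 and later, and the line-number covariate. First-line TTNT, and OS from lines 1 and 2, are not affected by A-B-A.

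The size is unknown. A median about 3–15% longer for 5–20% re-use rests wholly on assumed hazards and assumed re-use shares, and applies only to a line that a return can follow. It illustrates the effect and does not predict it. The point merits correction before analysis because it touches two primary objectives and is cheap to settle.

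**What to change.** Reconcile the principle and the bullets in 7.7.2 before the lines are built:

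- Date each line from the first record of a continuum, not of the substance.
- End a drug's continuum when a different line has started and the drug has no further record within a pre-specified gap. Set the gap length with the clinician and write it into the plan.
- Count a record of that drug after such a break as a new line, flagged as re-treatment.
- Do not start a new line for a continuing combination partner, or for a drug whose records continue without that gap alongside a later-added drug. Without this exemption, two drugs started more than 28 days apart but given together would produce a false third line and a false TTNT event.
- State that a break in one drug with no other line in between stays within the same line under this rule.
- Report line counts and TTNT with and without re-treatment lines.

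The cost is a few lines of protocol text and code. The small downside is that a late refill may be read as re-treatment, which the clinician consultation already planned in 7.9 can check. This changes an analysis definition only.

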In Finland, the mRCC treatment landscape has been shaped by the access and reimbursement status of medications. Here, publicly funded medicines are processed via two different access and reimbursement processes based on the route of administration: outpatient or oral medicines (patient acquires medicine with a prescription from the pharmacy) and hospital medicines (medicines administered at hospital, mainly intravenous medicines). For oral medicines, the Finnish Social Insurance Institution (Kela) reimburses the patient for the costs of outpatient medicines if the Pharmaceuticals Pricing Board (Hila) has confirmed the reimbursement of the medicine. For oral drugs, the marketing authorization holder is responsible for applying for reimbursement. The Finnish Medicines Agency (Fimea) is the national competent authority for regulating pharmaceuticals. Fimea is responsible for initiating the evaluation of hospital medicines to be used in Finland, and makes the initial health technology assessment (HTA). This HTA-evaluation is not made automatically for all new pharmacotherapies or indication extensions, but at the discretion of Fimea. Hospital medicines assessed by Fimea are further assessed by the Council for Choices in Health Care in Finland (COHERE Finland) to issue recommendations on services that should be included in the selection of public health services. Hospital medicines are paid by the municipalities that fund the hospital districts. The use of hospital medicines and prices may also vary greatly from region to region. Use of combination treatments is often problematic due to the Finnish reimbursement system because the combination partners may fall under different processes (eg. a combination of an oral drug and an intravenously administered drug).

PFIZER CONFIDENTIAL

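### The 28-day rule has no continued-use check, so a switch between two single drugs by day 28 is coded as a combination and lost as a TTNT event

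*Combined protocol and SAP*

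**What the plan says.** Section 7.7.2 of the combined protocol and SAP builds treatment lines from administration and prescription records:

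- Records are first joined within each drug: "For each active substance, single administrations/prescriptions are merged to treatment continuums".
- A pair is then tested on start dates alone: "if the first records of the two active substances are within 28 days, the treatment is considered as combination therapy of these two medications".
- Any other pair is split: "otherwise the two active substances are considered as two separate treatment lines".
- The start date needs only one record: "The initiation of the treatment line is defined as the date of first record (dosing or prescription) of the active substance".

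The same section opens with the principle that "line of treatment (LOT) changes when the active substance changes, as the treatments are mainly monotherapies and only a few options consist of two substances".

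Section 7.7.3 defines the TTNT proxy for progression-free survival as "time from initiation of the current treatment line until the initiation of the next treatment line (event), death (competing risk/event"), with censoring at end of study.

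Section 7.9 accepts that some lines may be misclassified and says a clinician will be consulted when lines are built. Section 7.8 adds a plausibility check of results by a clinical expert. Neither section states how an early switch is to be told apart from a combination.

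**The concern.** A drug that is stopped early and replaced, and a drug that is joined by a partner, give the same pattern of first records. The rule sees only that pattern, so it labels both as combinations. This contradicts the section's own principle that a change of substance changes the line.

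Three outputs are affected:

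- **Treatment patterns (primary objective 2).** The Sankey plot and the proportions per treatment type would show combinations that nobody gave. Since a prescription alone counts as a first record, a prescription replaced before use would also create one.
- **TTNT (primary objective 3).** The early switch is not an event. The patient's clock runs on to a later drug, death or censoring.
- **Line numbering.** One line is skipped, so each later line is numbered one too low. Line number is a Cox covariate (section 7.7.3), a stratifier for primary objectives 2 and 3 (section 7.2.3) and a reporting level for resource use (section 6.2).

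**Working it through.** **1. The plan's own figure.** The only size in the documents is the mRCC cohort in section 7.5: 0.20 × 1,100 = 220 and 0.50 × 1,100 = 550. Both reproduce. The documents give no switch rate, TTNT hazard or number of combinations.

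**2. The rule applied literally.** Take sunitinib first recorded on day 0, pazopanib on day t and nivolumab on day 200. Read the window as a gap of 28 days or less, and start a two-drug line at its earlier first record. The second reading is an assumption, because the plan does not say when a combination line starts.

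| t (days) | First line under the plan | First-line TTNT under the plan | TTNT if coded as a switch |
|---|---|---|---|
| 1 | sunitinib + pazopanib | 200 | 1 |
| 14 | sunitinib + pazopanib | 200 | 14 |
| 28 | sunitinib + pazopanib | 200 | 28 |
| 29 | sunitinib | 29 | 29 |

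The earliest switch that counts is on day 29. For t = 14 the plan also makes nivolumab line 2 instead of line 3, and the pazopanib line of 200 − 14 = 186 days does not exist. If a combination line started at the second drug instead, TTNT would be 186 days; the event on day 14 is lost either way. The rule is written for two substances and does not settle what happens when a third starts inside the window.

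**3. How many pairs the rule can label.** Table 3 (section 7.3) lists 6 oral and 2 intravenous substances, so there are 8 × 7 / 2 = 28 pairs. Those named as combinations in section 5 or 7.7.2 with both drugs in Table 3 are ipilimumab + nivolumab and nivolumab + cabozantinib: 2 pairs. The other 26, including all 6 × 5 / 2 = 15 oral-oral pairs, would also be labelled combinations when first recorded within 28 days of each other.

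**4. Possible size.** Assume a constant next-line hazard h per month, with the window w = 28 / 30.4 = 0.921 months.

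- Share of lines with a switch inside the window: 1 − exp(−h·w).
- Median shift: ignore death and give the second drug the same hazard. For t > w, the probability that the two-drug line has not ended is exp(−ht) + ∫₀ʷ h·exp(−hx)·exp(−h(t − x)) dx = exp(−ht)·(1 + h·w). The median therefore rises by ln(1 + h·w) / h over the true ln 2 / h.

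| h per month | Lines miscoded | True median (months) | Rise in median (months) | Relative rise |
|---|---|---|---|---|
| 0.03 | 2.7% | 23.1 | 0.91 | 4% |
| 0.06 | 5.4% | 11.6 | 0.90 | 8% |
| 0.10 | 8.8% | 6.9 | 0.88 | 13% |

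At day 28 the switch-free proportion would be 100% by construction, against 97.3% to 91.2% under the same hazards. For first lines, if all 220 to 550 patients were treated, about 6 (0.027 × 220) to 48 (0.088 × 550) patients would be affected. These counts are on the high side, because untreated patients are excluded from the mRCC cohort.

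**The case against.** **The safeguards may catch it.** The study is mainly descriptive, a clinician helps construct the lines, and an expert checks the results. An oral-oral pair in a Sankey plot is the kind of oddity such a check should find. This stands in part. But no override is written and the lines are defined post hoc, so any correction would be a case-by-case judgement that another analyst could not reproduce. A nivolumab-to-cabozantinib switch would look plausible and pass.

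**An early switch for intolerance is not progression.** True, but TTNT as defined counts any next line, whatever the reason. The same switch on day 29 would count.

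**The size is assumed and the median moves little.** This stands, and it limits the weight of the point.

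A reader might also infer more than the documents support:

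- *That the proxy is event-free for 28 days.* It is not. Death in that window remains an event or competing risk, and only switches are suppressed. Fast switchers also stay in the analysis, with times that are too long.
- *That planned partners arriving after day 28 are turned into false new lines.* Section 5 says "the combination partners may fall under different processes", but it is discussing access and reimbursement and mentions no delay between starts. Among the named combinations with both drugs in Table 3, only nivolumab + cabozantinib mixes routes.
- *That false combinations would dominate the combination category.* The documents give no count of true combinations, so there is no denominator.

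**Conclusion.** The concern holds for switches between two single drugs on days 1 to 28. It follows from sections 7.7.2 and 7.7.3 as written: each such switch is certain to be miscoded if the rule is followed literally. How often that happens is unknown. The 2.7% to 8.8% of lines and the rise of about 0.9 months in median TTNT rest on an assumed constant hazard of 0.03 to 0.10 per month; the median figure also ignores death and assumes equal hazards for successive drugs. On that basis the damage is mainly to early TTNT estimates, the reported combination category and line numbering, and less to the median. It is worth correcting before analysis because two primary objectives use these lines and the remedy is cheap. The fault is the missing continued-use condition; the documents give no ground for saying that 28 days is the wrong window.

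**What to change.** In section 7.7.2, keep the 28-day window and add one condition. A pair is a combination only if both drugs are first recorded on the same day, or the first drug's continuum carries on, with a further record after the second drug's first record. Every other pair is a switch, with the TTNT event on the date of the second drug's first record.

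- Do not let membership of a list of recognised pairs suffice. Nivolumab followed by cabozantinib can be a true sequence as well as a combination.
- Do not extend merging beyond day 28. Without a time limit or overlap test, that would join sequential lines which the plan now separates correctly.
- Settle pairs with a single record of each drug by a written rule, agreed with the clinician already consulted under section 7.9.
- Report how many pairs are reclassified, so that readers can see the effect.

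The cost is one extra condition in the code and a few single-record cases to adjudicate. The per-drug continuums are already being built, and section 7.9 expects start and end dates to be fairly precise, so no new data are needed.
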